#### 11.5. Stopping rules

Protocol HypErpolarised Xenon PuLmonary MRI in the Evaluation for EndobronChial Lung Volume Reduction Therapy CI: [name]

IRAS ID: 346681

IRAS ID: 346681

**REC Ref:** 

Not applicable.

#### 11.6. The Level of Statistical Significance

Statistical significance will be adapted depending on the novelty of results.

#### 11.7. Procedure for Accounting for Missing, Unused, and Spurious Data.

Complete case analysis will be performed at each time point. Missing data will be excluded.

#### 11.8. Procedures for Reporting any Deviation(s) from the Original Statistical Plan

Any deviations from the original statistical plan will be reported in the yearly trial report.

#### 12. DATA MANAGEMENT

The plan for the data management of the study is outlined below. There is not a separate Data Management document in use for the study.

#### 12.1. Source Data

Source documents are where data are first recorded, and from which participants' CRF data are obtained. These include, but are not limited to, hospital records (from which medical history and previous and concurrent medication may be summarised into the CRF), clinical and office charts, laboratory and pharmacy records, diaries, microfiches, radiographs, and correspondence.

CRF entries will be considered source data if the CRF is the site of the original recording (e.g. there is no other written or electronic record of data). All documents will be stored safely in confidential conditions. On all study-specific documents, other than the signed consent, the participant will be referred to by the study participant number/code, not by name.

#### 12.2. **Access to Data**

Direct access will be granted to authorised representatives from the Sponsor and host institution for monitoring and/or audit of the study to ensure compliance with regulations. Anonymised study data may be shared with approved third parties, including commercial organisations, to help improve imaging and treatment for people with COPD and other lung conditions. One example of this is that we may share anonymised Xenon MRI and CT scan data with researchers at the University of Oxford to support work on improving how the scans are analysed and matched together (a process called co-registration).

#### 12.3. **Data Recording and Record Keeping**

All study data will be stored using one or more of: password protected hard drives and NHS servers in anonymised form.

All documents containing personal data (the linkage spreadsheet and informed consent forms) will be stored securely in lockable cabinets and are only accessible by study staff and authorised personnel. Personal data such as personal addresses, postcodes, emails or telephone numbers of participants will be recorded electronically on spreadsheets for screened and enrolled patients that are accessed via an access-restricted computer. Personal data such as contact details and information that could lead to the identification of a participant (except for those who have consented to be approached for future research) will be destroyed as soon as it is practical to do so and no later than 12 months after the end of the study.

The study investigators are responsible for keeping documents encrypted where possible and kept securely to ensure that in case of an emergency, participants can be identified and contacted. Study data, including all standard of care EBV work up and follow-up taken from the medical notes, will be recorded in a de-identified manner directly into the study database; participants would not be identifiable from this. All participants will be identified by a code number (unique study ID number) on case report forms and any electronic databases. All source documents will have all identifiers removed and replaced by only the unique study ID number. This also applies to control participants.

The consent forms which link the study ID with the name of the participant will be stored in the Trial Master File, separately to the study data, and will be archived for a minimum of 5 years after the end of the study.

Pseudonymised imaging and study data will be transferred and stored on secure OUH NHS FT and servers and/or encrypted hard drives. This transfer will be performed in line with the Trust's information security handling rules Information Protection Policy (ouh.nhs.uk).

Pseudonymised imaging and study data may be used for commercial purposes, but only with consent from a participant.

#### 13. QUALITY ASSURANCE PROCEDURES

The study may be monitored, or audited in accordance with the current approved protocol, GCP, relevant regulations and standard operating procedures.

Data collected for the study may be reviewed for auditing and monitoring by authorised persons from the sponsor, regulatory authorities or their local host institutions to make sure that study is being carried out correctly. All investigators have a duty of confidentiality to research participants and nothing that could reveal their identity would be disclosed outside the research study team or site without specific consent from the research participant.

#### 13.1. Risk assessment

A risk assessment and monitoring are not deemed necessary. Any risks associated with the study assessments or data management have been outlined in the protocol (sections 13 and 17.3) and mitigations outlined.

Protocol
HypErpolarised Xenon PuLmonary MRI in the Evaluation for EndobronChial Lung
Volume Reduction Therapy

REC Ref:

### 13.2. Study monitoring

No monitoring required for this study.

#### 13.3. Study Committees

There are no oversight committees for this study as it is a small low-risk clinical research study.

#### 14. PROTOCOL DEVIATIONS

A study related deviation is a departure from the ethically approved study protocol or other study document or process (e.g. consent process or administration of study intervention) or from Good Clinical Practice (GCP) or any applicable regulatory requirements. Any deviations from the protocol will be documented in a protocol deviation form and filed in the study master file. A standard operating procedure will be in place describing the procedure for identifying non-compliances, escalation to the central team and assessment of whether a non-compliance /deviation may be a potential Serious Breach.

#### **15. SERIOUS BREACHES**

A "serious breach" is a breach of the protocol or of the conditions or principles of Good Clinical Practice which is likely to affect to a significant degree –

- (a) the safety or physical or mental integrity of the trial subjects; or
- (b) the scientific value of the research.

In the event of a serious breach is suspected, the Sponsor must be contacted within 1 working day. In collaboration with the C.I., the serious breach will be reviewed by the Sponsor and, if appropriate, the Sponsor will report it to the approving REC committee and the relevant NHS host organisation within seven calendar days.

#### 16. ETHICAL AND REGULATORY CONSIDERATIONS

#### 16.1. Declaration of Helsinki

The Investigator will ensure that this study is conducted in accordance with the principles of the Declaration of Helsinki.

### 16.2. Guidelines for Good Clinical Practice

The Investigator will ensure that this study is conducted in accordance with relevant regulations and with Good Clinical Practice.

Protocol
Hyperpolarised Xenon Pulmonary MRI in the Evaluation for EndobronChial Lung
REC Ref:

Volume Reduction Therapy

#### 16.3. **Approvals**

Following Sponsor approval of the protocol, informed consent form, participant information sheet and any proposed advertising material will be submitted to an appropriate Research Ethics Committee (REC), and HRA (where required) and host institutions for written approval.

The Investigator will submit and, where necessary, obtain approval from the above parties for all substantial amendments to the original approved documents.

#### 16.4. Other Ethical Considerations

There will be no involvement of vulnerable participants or participants who are unable to consent for themselves. If a participant loses capacity during their participation in the study, they will be withdrawn from the study, study data collected to that point will be retained and they may be replaced by a new participant.

The scan sequences and their images will be reviewed for quality control, utility, and to determine how best they may be improved. The researchers on reviewing the research scans will not record or report any abnormalities identified unless it is considered to be clearly in the participant's clinical interest. In such a case, the participant will be informed that there is a potential abnormality that warrants a referral for further assessment. This is to avoid unnecessary anxiety and consequences for false positive clinically insignificant abnormalities that may be detected by scanning even in healthy individuals. The participants will be made aware of this before being asked to give informed consent.

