Bronchoscopic deployment of EBV is the most extensively studied endobronchial LVR technique. The only two U.S. FDA-approved one-way valves currently in clinical use are the Zephyr (duckbillshaped) and Spiration (umbrella-shaped) valve systems. A meta-analysis of all eligible clinical trials investigating the benefits of these two valve systems have found significant improvement in FEV1 (an objective measure of airway obstruction), lung residual volume (RV, an objective measure of lung hyperinflation), 6-minute walk distance (6MWD, an objective measure of exercise capacity) and St. George's Respiratory Questionnaire (SGRQ, a patient-reported measure of quality of life) for at least 6 months when compared with standard medical treatment. 17 The largest multi-centre randomised controlled trial with 190 participants and the longest follow-up period of 12 months to date is the LIBERATE study using the Zephyr valve system. The mean difference between groups in LIBERATE at 12-month follow-up for post-bronchodilator (post-BD) FEV1 in percent change was +17.96%, RV -522 mL, 6MWD +39.31m, SGRQ score -7.05 (lower score indicating better health) and modified Medical Research Council Dyspnoea scale -0.8 points (mMRC, lower score indicating less breathlessness).18 Sustained benefits have been seen in FEV1, RV and 6MWD even after 3 years. 19 Pneumothorax, haemoptysis and post-procedural pneumonia were the most common complications, usually occurring within 6 months of EBV treatment. Endobronchial LVR treatment has also been reported to be an independent positive predictor of survival and reduces the number of COPD exacerbations.

The greatest benefit of EBV therapy in terms of FEV1 improvement is seen in those with heterogenous emphysematous disease and complete lobar fissure seen on quantitative CT (QCT) analysis. Incomplete lobar fissure is associated with interlobar collateral ventilation (CV) which may prevent EBV treatment from working. CV is the passage of air between alveoli through channels outside of the normal airways. Interlobar CV is more prevalent in COPD possibly due to the formation of new channels between lobes as a consequence of lung parenchymal destruction. The presence of interlobar CV allows movement of air from an untreated lobe to the EBV-targeted lobe, subsequently preventing collapse and volume reduction.

IRAS ID: 346681

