#### 7. STUDY DESIGN

This is a prospective, observational, cohort study comprising two patient cohorts – Cohort A – COPD patients, patients selected and planned for EBV treatment and Cohort B – COPD patients deemed unsuitable for EBV treatment due to presence of CV determined by the current gold standard assessments. The comparison of patterns of ventilation and/or physiological movement of gas using HPX-MRI will allow the assessment of collateral ventilation in the two cohorts of patients.

The study will recruit patients into the two cohorts through the local hospital-based COPD clinics. Participants who have been worked up for EBV therapy and their cases discussed at the local COPD multi-disciplinary team (MDT) meeting will be identified by the Clinician and informed of the study. COPD MDT comprises of respiratory physician(s), thoracic surgeon(s), thoracic radiologist(s), specialist nurse(s), respiratory physiotherapist(s) and occupational therapist(s).

The research team may participate in the MDT meetings where possible and may highlight potential patients suitable for the study to the clinicians. The clinicians involved in the MDT and the patients clinical care will inform the potential patients of the study and, if they agree, will provide them with the PIS and consent form, and ask their permission to be contacted by the research team to further discuss the study. If they agree to be contacted, a member of the research team will contact them, explain the study, assess eligibility and complete the informed consent form with the patient if they wish to participate. They will then invite them to undertake their baseline study visit locally at the Churchill Hospital, Oxford University Hospitals NHS Foundation Trust.

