#### 9.5. Blinding and code-breaking

There is no blinding in the study and no code breaking procedure.

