#### 11.2. Description of the Statistical Methods

All baseline characteristics and measures will be summarised overall and by cohort and group, using appropriate summary statistics.

ProtocolIRAS ID: 346681HypErpolarised Xenon PuLmonary MRI in the Evaluation for EndobronChial LungREC Ref:

Volume Reduction Therapy CI: [name]

We will aim to describe the prevalence of DV in patients with COPD being worked up for EBV. We will aim to describe the patterns of ventilation seen on HPX-MRI in patients with COPD who have been successfully treated with EBV and compare these findings with those who have not been successfully treated with EBV and those who have not been treated with EBV.

We will aim to examine the relationship between the presence of DV on HPX-MRI and EBV treatment success. We will also aim to correlate the presence of DV seen on HPX-MRI to the presence of CV following Chartis assessment and FC <95% on StratX. Where possible, we aim to examine the relevance of MRI perfusion to the success of EBV treatment and presence of DV. We will also aim to describe the physiological changes observed on HPX-MRI in those who have undergone EBV treatment and whether these changes are different in those who have been treated successfully to those who have not.

Continuous data, including questionnaire outcomes, will be summarised by group and time point using mean and standard deviation (or median and interquartile range if non normally distributed). Effects on outcomes over time (baseline visit and follow up visit) will be analysed using appropriate statistical models.

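### Nothing keeps the baseline HPX-MRI read from whoever classifies EBV success, so a DV-failure association could be created or inflated

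*Protocol*

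**What the plan says.** - **Blinding.** Section 9.5: "There is no blinding in the study and no code breaking procedure". Section 11.1 adds that no separate SAP is in use, so the protocol is the whole plan on this point.
- **Definition of success.** Section 8.1 (Cohort A) accepts atelectasis shown on imaging, better lung function or better symptoms, joined by and/or. It sets no size of change and does not say who classifies.
- **Order of events.** Under Section 7 the HPX-MRI may be done at the baseline visit. Under Section 9.7, Visit 2 in Cohort A falls six months after EBV. The scan therefore comes before both the valves and the success label.
- **Use of the label.** Section 11.2: "We will aim to examine the relationship between the presence of DV on HPX-MRI and EBV treatment success". Section 6 makes the contrast between successful and unsuccessful EBV part (b) of the primary outcome.
- **Release of scan findings.** Under Section 16.4 researchers neither record nor report abnormalities seen on the research scans "unless it is considered to be clearly in the participant's clinical interest". When the exception applies, "the participant will be informed that there is a potential abnormality that warrants a referral for further assessment".
- **Research team at the MDT.** Section 7: "The research team may participate in the MDT meetings where possible and may highlight potential patients suitable for the study to the clinicians".

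**The concern.** DV on HPX-MRI is the test under evaluation, and EBV success is the outcome it is meant to predict. The protocol gives a reason to expect failure when DV is present: Section 11.3 treats DV as suggesting collateral ventilation (CV), and Section 5 describes interlobar CV as "subsequently preventing collapse and volume reduction". Someone who knows the DV read therefore has an expectation about the outcome.

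A definition without thresholds leaves room for that expectation to act. A patient with a modest symptom gain and little change in lung function can be put on either side. If borderline DV-positive patients tend to be called failures and borderline DV-negative patients successes, an association appears that the lungs did not produce. With about 20 treated patients it could not be separated from a real one afterwards, and it would carry into the design of any later study.

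There is a second, weaker path. Because the scan precedes valve placement, a finding disclosed in that interval could lead to a change in an EBV plan already made. That would affect which treated patients are left to inform the DV-success question.

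**Working it through.** **The protocol's own figure.** Section 11.3 expects at least 20 of 40 patients to have DV/CV, from a prevalence above 50%. 0.50 × 40 = 20, which reproduces it. The protocol gives no power, effect size or fixed alpha, so there is no sample-size formula to check.

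**Can knowledge of the scan reach the success label?** Section 9.5 masks no one. Section 8.1 names no assessor. The scan precedes the outcome (Sections 7 and 9.7). No section keeps the DV read from the person who classifies success. The path is open as written.

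**How much could it matter?** This is an illustration, not an estimate. Inputs:
- 20 treated patients in Cohort A (Section 11.3).
- DV in 50% of them, so 10 DV-positive and 10 DV-negative. This borrows the figure for severe COPD in Section 11.3. Cohort A is selected for no evidence of CV, so its true share may be lower.
- True success of 50% in both groups, so no real link. Section 5 cites about 50% reaching the FEV1 target.
- A fraction *f* of labels moved toward expectation. This is assumed: 10%, 20% or 30%.

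If labels move in both directions:
- Apparent success, DV-positive: 0.50 × (1 − f)
- Apparent success, DV-negative: 0.50 + 0.50 × f
- Spurious odds ratio: odds of success in DV-negative divided by odds of success in DV-positive

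| f | DV-positive | DV-negative | Odds ratio | Chance that two-sided Fisher p ≤ 0.05 |
|---|---|---|---|---|
| 0 | 50% | 50% | 1.00 | 1.3% |
| 10% | 45% | 55% | 1.49 | 2.2% |
| 20% | 40% | 60% | 2.25 | 5.4% |
| 30% | 35% | 65% | 3.45 | 12.2% |

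Worked row, f = 20%: each group has 10 × 0.50 = 5 true successes and 5 true failures. 20% of 5 is one patient. So one DV-positive success is called a failure and one DV-negative failure a success, giving 4/10 v 6/10. The odds ratio is (6/4) ÷ (4/6) = 2.25.

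If only DV-positive successes are downgraded, the odds ratios for failure are 1.22, 1.50 and 1.86.

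The 0.05 level is assumed, because Section 11.6 does not fix one. Fisher's test is conservative at 10 v 10 (1.3% with no relabelling), so the distortion shows more in the estimate than in the test.

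**Can the scan change who is treated?** Under Section 7, cases have been discussed at the MDT before patients are identified for the study. Section 8.2 makes the decision for or against EBV a condition of cohort entry. The scan therefore cannot set the cohort. What remains is the interval between scan and valves. No section describes DV reads going to the MDT or the EBV operators in that interval, and none forbids it.

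**The case against.** The strongest defence is that much of the outcome is objective. Atelectasis and lung function are measured, the questionnaires are completed by participants (Section 9.6.3), and Section 7 expects most assessments at clinical follow-up before the research visit. This limits the exposure but does not remove it. Under an and/or rule with no thresholds, someone still decides which component counts and how much change is enough.

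A reader might go further and infer from Section 16.4 and the research team's place at the MDT that DV reads will reach the clinicians and decide who gets valves, so that the study ceases to be observational. The documents do not support this:
- Read whole, Section 16.4 restricts reporting. Its default of not recording abnormalities cannot be meant for DV, which must be recorded for Section 11.2. Its stated aim is to avoid alarm over clinically insignificant false positives.
- Its exception leads to informing and referring the participant. It names neither the MDT nor the EBV team.
- The team's stated role at the MDT is to point out candidates for the study.
- Section 5 gives other causes of DV, such as air trapping and peripheral airway obstruction, and Cohort A has already had CV ruled out by QCT and/or Chartis. DV in such a patient does not plainly meet the clinical-interest test.

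What stands is only a possibility: the exception does not separate study endpoints from incidental findings, and the scan comes before the valves. The documents give no basis for saying how often a plan would change.

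**Conclusion.** The concern holds for the success label. An open index test, a loosely defined and partly subjective outcome judged later, and no masked or named assessor together allow knowledge of DV to shape the outcome that DV is tested against. It bears on primary outcome (b) and the Section 11.2 DV-success analysis.

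In the illustration, moving two of 20 labels is enough for a spurious odds ratio of 2.25, and assumed relabelling of 10% to 30% in both directions gives 1.49 to 3.45. These values rest on the assumed 10/10 split, 50% success and relabelling rates. They show how sensitive so small a group is, not how much bias will occur. The defect itself follows from the text and needs none of these figures.

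The effect on treatment is a secondary possibility, to be logged and examined rather than assumed. The point should be fixed even in a pilot, because the remedy is cheap and the bias cannot be removed afterwards.

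**What to change.** 1. In Section 9.5, state that each participant's EBV success is classified and recorded without access to the HPX-MRI DV or ventilation reads.
2. In the same section, state that DV is read from images coded by study ID, by whoever already reads them, without knowledge of the success classification. Reading in batch is one way. If batches are read after success is recorded, this masking is essential, since otherwise the bias only changes direction.
3. Leave the clinical-interest exception in Section 16.4 as it stands. It protects participants and need not be narrowed to deal with this bias.
4. Add a CRF log of any disclosure of HPX-MRI findings before EBV or before success is recorded, and of any later change to the EBV plan.
5. In Section 11.2, report the DV-success analysis with and without the logged participants.

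The cost is wording in two sections, one log and one sensitivity analysis, with no extra patients or readers. The small downside is that DV results become available later.

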#### 16.5. Reporting

The CI shall submit an End of Study notification and final study report to the REC Committee (and any other parties as required).

#### 16.6. **Transparency in Research**

Prior to the recruitment of the first participant, the study will have been registered on a publicly accessible database.

Where the study has been registered on multiple public platforms, the trial information will be kept up to date during the trial, and the CI or their delegate will upload results to all those public registries within 12 months of the end of the trial declaration.

